**Cohort B and Cohort B1: SARS-CoV-2 RT-qPCR Positive at Baseline**

The endpoints are for all subjects who are seronegative at baseline (based on central lab test), unless stated otherwise.

***Cohort B Primary Efficacy Endpoint***

- Proportion of subjects who subsequently develop signs and symptoms (broad-term) within 14 days of a positive RT-qPCR at baseline or during the EAP

***Cohort B Key Secondary Efficacy Endpoints***

- Number of weeks of symptomatic SARS-CoV-2 infection (broad-term) within 14 days of a positive RT-qPCR at baseline or during the EAP
- Number of weeks of high viral load  $>4$  ( $\log_{10}$  copies/mL) in NP swab samples during the EAP

***Cohort B and Cohort B1 Other Secondary Efficacy Endpoints***

- Proportion of subjects who subsequently develop signs and symptoms (CDC definition) within 14 days of a positive RT-qPCR at baseline or during the EAP
- Proportion of subjects who subsequently develop signs and symptoms (strict-term) within 14 days of a positive RT-qPCR at baseline or during the EAP
- Number of weeks of symptomatic SARS-CoV-2 infection (CDC definition) within 14 days of a positive RT-qPCR at baseline or during the EAP
- Number of weeks of symptomatic SARS-CoV-2 infection (strict-term) within 14 days of a positive RT-qPCR at baseline or during the EAP
- Proportion of subjects with viral load  $>4$  ( $\log_{10}$  copies/mL) in NP swab samples during the EAP
- Change in viral load ( $\log_{10}$  copies/mL) from baseline to day 8 visit in NP swab samples
- Change in viral load ( $\log_{10}$  copies/mL) from baseline to day 15 visit in NP swab samples
- Time-weighted average change from baseline in viral load ( $\log_{10}$  copies/mL) in NP swab samples until the day 22 visit.
- Area under the curve (AUC) in viral load ( $\log_{10}$  copies/mL) in NP swab samples from baseline to the first confirmed negative test
- Maximum SARS-CoV-2 RT-qPCR viral load ( $\log_{10}$  copies/mL) in NP swab samples during the EAP
- Number of medically attended visits in emergency rooms or urgent care centers related to RT-qPCR confirmed SARS-CoV-2 infection that has an onset at baseline or during the EAP
- Proportion of subjects requiring medically attended visits in emergency rooms or urgent care centers related to a RT-qPCR confirmed SARS-CoV-2 infection that has an onset at baseline or during the EAP
- Proportion of subjects hospitalized related to a RT-qPCR confirmed SARS-CoV-2 infection that has an onset at baseline or during the EAP

- Number of days of hospital and ICU stay in subjects hospitalized for a RT-qPCR confirmed SARS-CoV-2 infection that has an onset at baseline or during the EAP
- Number of days missed for daily responsibilities (where applicable), including work (employed adults) or school (students), or family obligations/responsibilities (childcare or eldercare) due to a RT-qPCR confirmed SARS-CoV-2 infection that has an onset at baseline or during the EAP
- Proportion of subjects with at least 1 COVID-19 related hospitalization or emergency room visit associated with a positive RT-qPCR at baseline or during the EAP, or all-cause death

*Additional Cohort B1 Secondary Efficacy Endpoints*

- Proportion of subjects who subsequently develop signs and symptoms (broad-term) within 14 days of a positive RT-qPCR at baseline or during the EAP
- Number of weeks of symptomatic SARS-CoV-2 infection (broad-term) within 14 days of a positive RT-qPCR at baseline or during the EAP
- Number of weeks with high viral load  $>4$  ( $\log_{10}$  copies/mL) in NP swab samples at during the EAP

*Cohort B and Cohort B1 Secondary Safety Endpoints*

- Proportion of subjects with TEAEs and severity of TEAEs
- Incidence and severity of symptomatic SARS-CoV-2 infection in both the EAP and follow-up periods

*Cohort B and Cohort B1 Pharmacokinetic and Immunogenicity Endpoints*

- Concentrations of REGN10933 and REGN10987 in serum over time and selected PK parameters in both seronegative and seropositive subjects (based on baseline central lab test)
- Immunogenicity as measured by ADAs and NAbs to REGN10933 and REGN10987 over time in both seronegative and seropositive subjects (based on baseline central lab test)

**Procedures and Assessments****Screening/Baseline Procedures:**

The following procedures will be performed for the purpose of determining study eligibility or characterizing the baseline population: demographics (eg, age, sex, race, weight, height, etc), medical history, local diagnostic assay for SARS-CoV-2, query for risk for SARS-CoV-2 infection, and household assessment in which subjects will be asked to provide general information about the household members.

The investigator or sub-investigator will verify that the subject tests negative or positive by a local diagnostic assay for SARS-CoV-2 (eg, molecular assay such as RT-PCR assay for SARS-CoV-2 or a SARS-CoV-2 antigen test using an appropriate sample such as NP, nasal, OP, or saliva). The local diagnostic assay for SARS-CoV-2 must be considered acceptable for clinical use by local standards. If the test has not been approved or received EUA issued by the US FDA or by the equivalent local health authority, then the Sponsor should be consulted. The use of a RT-PCR assay is highly recommended.

The local diagnostic test result, specimen type (eg, nasal swab), assay type, and date of test will be recorded in the eCRF. The sample type collected is dependent on local lab requirements.

**Efficacy Procedures:**

Nasopharyngeal Swab SARS-CoV-2 RT-qPCR Test (Central Lab): Nasopharyngeal swab sample will be collected from subjects to determine presence or absence of SARS-CoV-2 virus and to determine the relative quantification in viral load.

**COVID-19 Symptomology (Broad Term, Strict Term, CDC definition):**

During each scheduled or unscheduled visit/contact, the investigator or sub-investigator, or designee (ie, nurse practitioner in countries where allowed by local law) will query the subject and/or subject's parent or guardian about adverse events the subject is experiencing or has experienced since the last visit/contact (eg, within the prior week if it is a weekly scheduled visit) and ask about all of the signs and symptoms associated with these adverse events including the start date, end date and severity of each. The investigator should avoid querying the subject and/or subject's parent or guardian by running a check-list of signs and symptoms, but rather allow the subject and/or subject's parent or guardian to spontaneously report everything that they presented.

All signs and symptoms related to the AEs, along with the corresponding start date, end date and severity should be documented in the subject's medical records (source document). As signs and symptoms may appear and resolve on different days and may precede or occur after the collection of NP swab sample for the SARS-CoV-2 RT-qPCR test, it is important that this detailed information be captured in the source document.

Independent of the results (positive or negative) of the SARS-CoV-2 RT-qPCR tests performed on samples collected from study subjects during the weekly or unscheduled visits, all adverse events must be documented in the AE CRF. Signs and symptoms related to the adverse events reported in the AE CRF and confirmed to be temporally related to a positive SARS-CoV-2 RT-qPCR test collected from the subject's NP swab sample will be reported on a separate CRF (individual sign or symptom with start date and end date, and associated severity).

---

Strict-term COVID-19 signs and symptoms, defined as:

- fever ( $\geq 38^{\circ}\text{C}$ ) PLUS  $\geq 1$  respiratory symptom (sore throat, cough, shortness of breath);  
OR
- 2 respiratory symptoms (sore throat, cough, shortness of breath);  
OR
- 1 respiratory symptom (sore throat, cough, shortness of breath) PLUS  $\geq 2$  non-respiratory symptoms (chills, nausea, vomiting, diarrhea, headache, conjunctivitis, myalgia, arthralgia, loss of taste or smell, fatigue or general malaise).

- Broad-term COVID-19 signs and symptoms: defined as any of the 23 symptoms (listed earlier in the Objectives) or fever ( $\geq 38^{\circ}\text{C}$ ).
- The CDC definition: defined as at least 2 of the following symptoms: fever (measured or subjective), chills, rigors, myalgia, headache, sore throat, nausea or vomiting, diarrhea, fatigue, congestion or runny nose OR Any 1 of the following symptoms: cough, shortness of breath, difficulty breathing, new olfactory disorder, new taste disorder OR Severe respiratory illness with at least 1 of the following, clinical or radiographic evidence of pneumonia, ARDS.

**Medically Attended Visits:** Subjects and/or their parent/guardian (as appropriate) who become SARS-CoV-2 RT-qPCR positive will be queried on any SARS-CoV-2 infection-related medically attended visits to the ED, UCC, or hospitalization. The assessment of medically attended visits to ED, UCC or hospitalization will be performed from the time the subject first becomes SARS-CoV-2 RT-qPCR positive or from the time they develop symptoms suspected to be COVID-19 (later confirmed by RT-qPCR positive results) until the subject has had 2 negative tests or COVID-19 related symptoms have resolved (whichever lasts longer), or of until the end of study visit.

**Absenteeism Assessment:** Subjects and/or their parent/guardian who are or become SARS-CoV-2 RT-PCR positive during the EAP will be queried on any SARS-CoV-2 infection-related absenteeism. Data include absenteeism (where applicable) defined as number of days missed for daily responsibilities, including work (employed adults) or school (students), daycare, or family obligations/responsibilities (childcare or eldercare) due to COVID-19.

#### **Safety Procedures:**

**Targeted Physical Examination and Vital Signs:** The targeted physical examination and vital signs include measurements of body temperature, blood pressure (measured after the subject has been resting quietly for at least 5 minutes and may be obtained from a seated or supine position), pulse rate, and respiratory rate, and examination of the oropharynx, skin, heart, lungs and any other system(s) depending on any complaints or concerns expressed by the subjects.

**Laboratory Testing:** samples for blood chemistry, hematology, and urinalysis (only for adolescent/adult subjects) will be collected and analyzed. For all women of childbearing potential, a urine pregnancy test will be performed onsite and any positive urine pregnancy test will be confirmed with a serum pregnancy test at the central laboratory.

---

---

**Other Procedures:**

Drug Concentration and Immunogenicity measurements: Dense sample and sparse sample collection for drug concentration measurement will be performed in subsets of subjects. Samples for ADA and NAb assessment will be collected at various times throughout the study. Any unused serum samples may be used for exploratory research.

Serological Assays for Endogenous Anti-SARS-CoV-2 Antibodies: In order to assess the impact of baseline humoral immunity/antibody response to SARS-CoV-2 on REGN10933+REGN10987 efficacy to prevent SARS-CoV-2 infection, serum anti-SARS-CoV-2 will be measured at baseline, including but not limited to those which detect antibodies against the S protein and/or the N protein and/or neutralization assays. Samples will be collected from adult and pediatric subjects (<18 years).

Exploratory Pharmacodynamic/Biomarker and Serum/Plasma Samples for Research: Samples for assessment of pharmacodynamic and exploratory research will be collected from adult and adolescent subjects.

Pharmacogenomic Analysis (Optional): Adult and pediatric subjects (<18 years and >10 kg) subjects may participate in an optional genomics sub-study (separate informed consent required). Blood sample for RNA and DNA will be collected for this substudy.

---

**Statistical Plan****Justification of Sample Size**

An administrative assessment for assumption verification and sample size estimation for cohort A will be conducted using unblinded descriptive analyses without performing any formal statistical hypothesis testing. Analyses will be conducted in the group of cohort A subjects randomized from study initiation through the date of randomization that are associated with 30 RT-PCR events amongst cohort A seronegative subjects during the EAP (approximately 600 subjects overall regardless of baseline serology status[eg, seronegative, seropositive, or other (eg, borderline or undetermined, etc)]). The subjects evaluated in this descriptive analysis will not be included for the final efficacy analyses, however, these subjects will be included in the safety analyses. To maintain operational efficiencies and because of the progressive rollout of SARS-CoV-2 vaccination which may change the dynamics of virus transmission/infection in the near future, enrollment into the study will not be paused while the administrative assessment is performed and it is estimated that the total enrollment may reach approximately 3500 subjects. The following justification of sample size in cohort A with the assumption of reduction of symptomatic infection is based on the results from the administrative assessment described below. For the purpose of the study analysis, cohort A and cohort B are independent with separate type I error control for each cohort.

***Cohort A: Adult and Adolescent Subjects (≥12years) Who Are SARS-CoV-2 RT-qPCR Negative***

In cohort A, subjects are randomized in a 1:1 allocation ratio to REGN10933+REGN10987 or placebo. The primary hypothesis is the reduction in the proportion of symptomatic RT-qPCR (broad-term) confirmed SARS-CoV-2 infections in seronegative subjects. To calculate the sample size required to achieve at least 90% power for seronegative subjects in cohort A, it is assumed that the statistical hypothesis will be tested in a 2-sided test. Based on the administrative assessment results among 409 seronegative subjects in cohort A, a 50% reduction of infections (symptomatic or asymptomatic) compared to the placebo group and a 100% reduction of symptomatic infections compared to placebo group were observed. Due to the small sample size in the

---

administrative assessment, it was assumed, for the purpose of assessing study power, that an approximately 50% reduction or greater in symptomatic infections compared to the placebo group will be expected for the final primary efficacy analysis.

In this household study design, the number of subjects per household, the correlation between subjects and symptomatic infection rates within a household are unknown. To detect a relative risk of 0.5 (ie, 50% reduction of the assumed 10% attack rate in the placebo arm), equivalent to an odds ratio of 0.47, power was also calculated compared to the boundary p-value of 0.05 based on 2000 simulations in 1248 subjects from 430 households (ie, assuming an average household size of 2.9 seronegative subjects by varying degrees of correlation within household. In all cases, the power of the study is >90% using a generalized linear model with the generalized estimation equation (GEE) approach and assuming a compound symmetry covariance matrix.

At least 1980 subjects will need to be enrolled in cohort A to have a minimum of 1248 seronegative subjects, assuming that 10% of subjects drop out, 30% of subjects are seropositive at baseline.

***Cohort A1: Pediatric Subjects (<12 years) with SARS-CoV-2 RT-qPCR Negative***

Approximately up to a total of 250 pediatric subjects (<12 years) will be enrolled in this study. Of the 250 subjects, 90% (225/250) are expected to be enrolled in this cohort (ie, central lab RT-qPCR negative at baseline) for evaluating the drug concentration and exposure, and safety. The actual number of subjects in this cohort will depend on the actual percentage of subjects with a baseline negative RT-qPCR enrolled. No statistical hypothesis tests will be performed.

***Cohort B: SARS-CoV-2 RT-qPCR Positive***

The primary endpoint in asymptomatic, seronegative subjects in cohort B is the proportion of subjects who subsequently develop signs and symptoms (broad term) within 14 days of a positive RT-qPCR test result at baseline or during the EAP.

The sample size of cohort B is based on the frequency of finding positive subjects while enrolling cohort A and assumes that approximately 10% of subjects in a household are already positive for SARS-CoV-2 by RT-qPCR at baseline. Among approximately 3500 adult and adolescent subjects that are anticipated to be enrolled in cohort A or cohort B, the number of subjects expected in cohort B is approximately 220 or greater, including 200 seronegative subjects. Assuming that 50% of infected placebo subjects at baseline will develop symptoms, 200 seronegative subjects in cohort B will provide >90% power to detect a relative risk of 0.5, using a 2-sided Fisher's exact test at an alpha level of 0.05.

***Cohort B1: Pediatric Subjects (<12 years) with SARS-CoV-2 RT-qPCR Positive***

Approximately up to a total of 250 pediatric subjects (<12 years) will be enrolled in this study. Of 250 subjects, 10% (25/250) are expected to be enrolled in this cohort (ie, central lab RT-qPCR positive at baseline) for evaluating the drug concentration and exposure, and safety. The actual number of subjects in this cohort will depend on the actual percentage of subjects with a baseline positive RT-qPCR enrolled. No statistical hypothesis tests will be performed.

---

**Efficacy Analysis Sets*****Seronegative Modified Full Analysis Set (Seronegative mFAS-A) – Cohort A***

The seronegative modified full analysis set for cohort A (seronegative mFAS-A) includes all randomized subjects aged 12 years and older who are laboratory confirmed negative for SARS-CoV-2 (per central lab PCR test) and who test negative for antibodies for SARS-CoV-2 (per central lab serology testing) at baseline.

Subjects included in the administrative assessment analysis are excluded from the seronegative mFAS-A population.

Subjects will be analyzed based on the randomized treatment assignment. The seronegative mFAS-A population is the primary analysis population for the primary and secondary endpoints for cohort A of this study unless specified otherwise.

***Seronegative Modified Full Analysis Set (Seronegative mFAS-A1) – Cohort A1***

The seronegative modified full analysis set for cohort A1 (seronegative mFAS-A1) includes all randomized subjects aged less than 12 years who are laboratory confirmed negative for SARS-CoV-2 (per central lab PCR test) and who test negative for antibodies for SARS-CoV-2 (per central lab serology testing) at baseline.

Subjects will be analyzed based on the randomized treatment assignment. The efficacy endpoints for cohort A1 will be analyzed using the seronegative mFAS-A1 unless specified otherwise.

***Seronegative Modified Full Analysis Set (Seronegative mFAS-B) – Cohort B***

The seronegative modified full analysis set for cohort B (seronegative mFAS-B) includes all randomized subjects aged 12 years and older who have laboratory confirmed positive tests at baseline for SARS-CoV-2 RT-qPCR and negative SARS-CoV-2 serology (both based on central lab testing) and are asymptomatic at baseline. Subjects will be analyzed based on the randomized treatment assignment. The primary and secondary efficacy endpoints for cohort B will be analyzed using the seronegative mFAS-B unless specified otherwise.

***Seronegative Modified Full Analysis Set (Seronegative mFAS-B1) – Cohort B1***

The seronegative modified full analysis set for cohort B1 (seronegative mFAS-B1) includes all randomized subjects aged less than 12 years who have laboratory confirmed positive tests at baseline for SARS-CoV-2 RT-qPCR and negative SARS-CoV-2 serology (both based on central lab testing) at baseline. Subjects will be analyzed based on the randomized treatment assignment. The efficacy endpoints for cohort B1 will be analyzed using the seronegative mFAS-B1 unless specified otherwise.

**Primary Efficacy Analysis (Cohort A)**

The primary efficacy endpoint will be analyzed in the seronegative mFAS-A population. In order to account for the correlation among subjects within a household and control the associated type 1 error inflation, a generalized linear model will be used to estimate the odds ratio between the treatment groups by using the GEE approach. This model estimates a single within-household correlation coefficient. The model will include the fixed category effects of treatment group (placebo versus REGN10933+REGN10987), region (US vs ex-US), and age ( $\geq 12$  to  $< 50$ ,  $\geq 50$  years). The model will use a compound symmetry covariance matrix and estimate the odds ratio between the treatment groups and corresponding 95% CI and p-value. If the GEE model fails to converge due to most households containing only a single study subject in

---

seronegative mFAS-A or the percentage of households with only a single study subject is 70% or more, then a logistic regression model will be used, with treatment, region, and age group as fixed effects.

Subjects with COVID-19 symptoms that are missing a central lab determined RT-qPCR test during the EAP (eg. are too sick to go to the study site) but have a positive SARS-COV-2 test from a local lab (eg. in the hospital) will be considered as having a symptomatic infection if any of the symptoms occurred within 14 days of the positive SARS-COV-2 test.

Additional sensitivity analyses for missing data are described in the protocol.

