#### 11.2.1. Cohort A: Adult and Adolescent Subjects ( $\geq 12$ years) Who Are SARS-CoV-2 RT-qPCR Negative at Baseline

In cohort A, subjects are randomized in a 1:1 allocation ratio to REGN10933+REGN10987 or placebo. The primary hypothesis is the reduction in the proportion of symptomatic RT-qPCR (broad-term) confirmed SARS-CoV-2 infections in seronegative subjects. To calculate the sample size required to achieve at least 90% power for seronegative subjects in cohort A, it is assumed that the statistical hypothesis will be tested in a 2-sided test. Based on the administrative assessment results among 409 seronegative subjects in cohort A, a 50% reduction of infections (symptomatic or asymptomatic) compared to the placebo group and a 100% reduction of symptomatic infections compared to placebo group was observed. Due to the small sample size in the administrative assessment, it is assumed, for the purpose of calculating study power, that an approximately 50% reduction or greater in symptomatic infections compared to placebo group will be expected for the final primary efficacy analysis.

In this household study design, the number of subjects per household, the correlation between subjects and symptomatic infection rates within a household are unknown. To detect a relative risk of 0.5 (ie, 50% reduction of the assumed 10% attack rate in the placebo arm), equivalent to an odds ratio of 0.47, power was calculated compared to the p-value of 0.05 based on 2000 simulations in 1248 subjects from 430 households (ie, assuming an average household size of 2.9 seronegative subjects). [Table 9](#) provides power calculations by varying degrees of correlation within household. In all cases, the power of the study is >90% using a generalized linear model with the generalized estimation equation (GEE) approach and assuming a compound symmetry covariance matrix.

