**Table 9: Simulated Power for Household Design (1248 Subjects over 430 Households)**

Placebo Attack Rate	REGN10933+REGN10987 Attack Rate	Correlation within Household	Average Odds Ratio REGN10933+REGN10987 versus Placebo	Power
10%	5%	0.1	0.485	0.914
10%	5%	0.2	0.485	0.934
10%	5%	0.3	0.480	0.956
10%	5%	0.4	0.481	0.972
10%	5%	0.5	0.476	0.983
10%	5%	0.6	0.478	0.999

At least 1980 subjects will need to be enrolled in cohort A to have a minimum of 1248 seronegative subjects, assuming that 10% of subjects drop out and 30% of subjects are seropositive at baseline.

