#### **11.4.3.1.1. Sensitivity Analyses**

Robustness of the primary analyses results in cohort A and cohort B will be assessed through sensitivity analyses as follows:

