#### Seronegative mFAS-A Subjects

The overall type I error will be controlled for the primary hypothesis in cohort A based on a 2-sided test at an alpha level of 0.05 as follows:

H0: There is no treatment difference between REGN10933+REGN10987 and placebo in the proportion of subjects with a symptomatic RT-qPCR confirmed SARS-CoV-2 infection during EAP.

H1: There is a treatment difference between REGN10933+REGN10987 and placebo in the proportion of subjects with a symptomatic RT-qPCR confirmed SARS-CoV-2 infection during the EAP

If the primary efficacy endpoint in cohort A is statistically significant, the alpha level of 0.05 will be released for the key secondary endpoints in cohort A. The hierarchical testing sequence for key secondary efficacy endpoints is presented in [Table 10](#).

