5.7.1. Analysis of Primary Efficacy Variables

Cohort A

The Cohort A primary efficacy endpoint described in Section 4.5.1 will be analyzed in the seronegative mFAS-A population. All post-baseline efficacy assessments obtained in the EAP will be included for the primary analysis.

In order to account for the correlation among subjects within a household and control the associated type 1 error inflation, a generalized linear model will be used to estimate the odds ratio between the treatment groups by using the GEE approach (See Appendix 10.4 for an example of SAS procedure). This model estimates a single within-household correlation coefficient. The model will include the fixed category effects of treatment group (placebo versus REGN10933+REGN10987), region (US versus ex-US), and age (≥ 12 to < 50 , ≥ 50 years). The model will use a compound symmetry covariance matrix and estimate the odds ratio between the treatment groups and corresponding 95% CI and p-value.

If the GEE model fails to converge due to most households containing only a single study subject in seronegative mFAS-A or the percentage of households in Cohort A with only a single study subject is 70% or more, then a logistic regression model will be used with treatment, region, and age group as fixed effects. The threshold of 70% was based on simulations of within-household correlation which show the type I error rate is inflated and the power is decreased when the

proportion of single-subject households is high (details provided in Section 6.6). If the logistic regression model does not converge, an exact logistic regression will be used. The estimates of odds ratio, the corresponding 95% CI and p-value will be provided from logistic regression (or exact logistic regression) for comparison of REGN10933+REGN10987 against placebo group.

In Cohort A, a subject will be considered having a symptomatic RT-qPCR confirmed SARS-CoV-2 infection (broad-term) during the EAP if any of the post-baseline RT-qPCR results during the EAP are positive with at least one symptom within 14 days of a positive RT-qPCR result (Section 4.5).

Cohort B

The Cohort B primary efficacy endpoint described in Section 4.5.5 will be analyzed in the seronegative mFAS-B population. The same statistical methods as described for Cohort A will be used to obtain the estimate of odds ratio and p-value for comparison between the treatment groups.

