10.4. Example of SAS Procedures for Primary Analysis and Missing Data Imputations by FCS

Primary Analysis - GEE Model

Below is an example of SAS code using a generalized linear model to estimate the odds ratio between the treatment groups with the generalized estimation equation (GEE) approach after 100 imputations.

```
proc genmod data=DATA_IN;
class treatment(ref='0') Age_group region; /*eg.treatment= 0:placebo */
by _imputation_;
model response(event='1') =treatment region age_group/dist=bin link=logit;
repeat subject=household_id/type=cs;
lsmeans treatment/diff om cl ilink;
ods output diffss=logOR geeexchcorr=icc;
run;
```

Primary Analysis - Logistic Regression Model

Below is an example of SAS code using a logistic regression model instead of using GEE approach when the percentage of households with a single study subject is 70% or more to estimate the odds ratio between the treatment groups after 100 imputations.

```
proc genmod data=DATA_IN descending;
class treatment(ref='0') Age_group region;
by _imputation_;
model response(event='1') =treatment region age_group/dist=bin link=logit;
lsmeans treatment/diff om cl ilink;
ods output diffss=logOR ParameterEstimates=parameterestimates;
```

run;

Missing Data Imputations – FCS

Assume the missing RT-qPCR test results occurred across Visit 5 (Day 8) to Visit 8 (Day 29) (e.g. 1=positive vs 0=negative). An example of SAS code for FCS MI with the random seed=2069 is presented below.

```
proc mi data=DATAIN out=DATAOUT seed=2069 nimpute=100;
class treatment age_group region v5 v6 v7 v8;
var treatment age_group region v5 v6 v7 v8;
fcs logistic(v5/LIKELIHOOD=AUGMENT);
fcs logistic(v6/LIKELIHOOD=AUGMENT);
fcs logistic(v7/LIKELIHOOD=AUGMENT);
fcs logistic(v8/LIKELIHOOD=AUGMENT);
run;
```

After FCS MI to generate 100 complete datasets, each subject's overall RT-qPCR test status during the EAP can be determined by any of imputed value V5 to V8 is equal to 1. The same model using GEE approach or logistic regression for the primary analysis will be applied.

The results from the 100 analyses will be combined using Rubin's formulae through PROC MIANALYZE procedure shown below.

```
proc mianalyze data=logOR;
ods output parameterestimates=final_logor;
modeleffects estimate;
stderr stderr;
run;
```

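### The synopsis promises missing-data sensitivity analyses for the primary endpoint that neither document contains, and the SAP gives conflicting rules for missing primary-endpoint data

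*Protocol*

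**What the plan says.** The protocol synopsis, under Primary Efficacy Analysis (Cohort A), closes with "Additional sensitivity analyses for missing data are described in the protocol". Protocol 11.4.3.1.1 opens with "Robustness of the primary analyses results in cohort A and cohort B will be assessed through sensitivity analyses as follows" and gives two analyses: excluding subjects positive within 72 hours of dosing (Cohort A only), and excluding non-GCP-compliant sites (both cohorts). SAP 5.7.1.1 repeats these two, and SAP Appendix 10.1 lists no others.

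The seronegative mFAS-A (Protocol 11.3.1, SAP 3.1) is all randomised, PCR-negative, seronegative subjects outside the administrative assessment. Completing the efficacy assessment period (EAP) is not required.

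On missing primary-endpoint data the SAP has three statements:

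- **Section 5.7.1** (with Protocol 11.4.3.1): a Cohort A subject is an event "if any of the post-baseline RT-qPCR results during the EAP are positive with at least one symptom" within 14 days. The one missing-data rule is that symptoms plus a positive local-laboratory test also count. SAP 6.2 refers the reader back to this section for missing RT-qPCR results.
- **Appendix 10.1**: for the primary endpoint, a missing RT-qPCR becomes positive when a broad-term symptom falls within 14 days of the missed visit. No local test is needed.
- **Appendix 10.4**: the code headed as the primary analysis fits the model "with the generalized estimation equation (GEE) approach after 100 imputations", with a `by _imputation_` statement. SAP 5.7.3 specifies multiple imputation only for the any-infection key secondary endpoint.

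The sample size is set "assuming that 10% of subjects drop out and 30% of subjects are seropositive at baseline".

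**The concern.** An event has to be observed, and the analysis set keeps everyone. Under 5.7.1, a subject who leaves on day 5 with no positive test therefore stays in the denominator as event-free to Day 29. The plan never says so, and no analysis asks whether the primary result depends on it. The single time-to-event item, a Kaplan-Meier display of time to first symptom, carries no estimate or test.

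Two things are at stake. First, the three SAP statements can classify the same subject differently on the confirmatory endpoint, so two programmers following one SAP could obtain different primary results. Second, departure could depend on outcome or arm. RT-qPCR results are not blinded during the study (Protocol 3.2.3), and in the administrative assessment 10.3% of placebo and 5.4% of active subjects were infected at day 8 (Protocol 3.2.6). Protocol 7.3 itself warns about the effect of excessive withdrawal on interpretability.

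**Working it through.** **1. The rules side by side.** Two Cohort A subjects, neither with a positive test on file:

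| Subject | SAP 5.7.1 | Appendix 10.1 | Appendix 10.4 |
|---|---|---|---|
| Negative on day 8, cough on day 12, misses the day 15 swab, no local test, leaves | Non-event | Event | Run on imputed data; PCR status varies by dataset |
| Leaves on day 5, no symptoms, no later swab | Non-event (implied) | Non-event (nothing to convert) | PCR status imputed, symptoms not, so the symptomatic outcome is undefined |

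The imputation code in 10.4 fills only visits V5 to V8 of PCR status. That yields any infection (5.7.3), but not symptomatic infection. For Cohort B it helps even less: the baseline PCR is already positive, so what a leaver lacks is symptom follow-up.

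**2. The plan's own figures.** Inputs from Protocol 11.2.1 and 11.4.4: a test "based on a 2-sided test at an alpha level of 0.05 as follows", a "50% reduction of the assumed 10% attack rate in the placebo arm", 1248 seronegative subjects, 10% dropout and 30% seropositive.

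- Enrolment: 1248 / (0.90 × 0.70) = 1981, against the stated 1980.
- Power, 624 per arm, 10% vs 5%, clustering ignored: 0.919 (two proportions) or 0.908 (Wald on the log odds ratio), against 0.914 in Table 9 at correlation 0.1. The claim "In all cases, the power of the study is >90% using a generalized linear model" is reproduced.

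**3. Size of the unexamined group.** 1980 × 0.70 = 1386 seronegative subjects, or 693 per arm. 10% is 69 leavers per arm, leaving 624 followed. Events among those followed: 624 × 0.10 = 62 and 624 × 0.05 = 31.

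**4. Tipping point at 10% vs 5%.** Wald test, log OR = ln[b/(693−b)] − ln[a/(693−a)], SE = √(1/a + 1/b + 1/(693−a) + 1/(693−b)), with a placebo and b active events. Leavers are assumed to go before any event; clustering is ignored.

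| Assumption about leavers | Events, placebo vs active | OR | p |
|---|---|---|---|
| All non-events | 62 vs 31 | 0.48 | 0.001 |
| Both arms at the placebo rate (7 of 69 each) | 69 vs 38 | 0.52 | 0.002 |
| 12 of 69 active (17%), no placebo | 62 vs 43 | 0.67 | 0.055 |
| 18 of 69 active (26%), placebo at 10% | 69 vs 49 | 0.69 | 0.055 |

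An uncorrected chi-square gives 0.0009 for 62 vs 31 and 0.054 for 62 vs 43.

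**5. Equal dropout costs little power.** Scored rates become 9% and 4.5% on 693 per arm: power 0.917.

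**6. Unequal dropout (assumed range).** Placebo dropout 10%, true relative risk 0.5, scored relative risk = 0.05 × (1 − d) / 0.09 for active dropout d:

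- d = 5%: 0.53; d = 15%: 0.47; d = 20%: 0.44.
- With no true effect at 10% and d = 20%: 9% vs 8%, SE = √[(0.09 × 0.91 + 0.08 × 0.92)/693] = 0.0150, standardised difference 0.01/0.0150 = 0.67, rejection probability about 10% instead of 5%.

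**7. Lower placebo rate.** The administrative assessment saw 8/223 (3.6%) on placebo and 0/186 on active. Taking 3.6% with the plan's relative risk of 0.5 (an assumption): 624 × 0.036 = 22 and 624 × 0.018 = 11, Wald p = 0.057. Adding 2 events among the 69 placebo leavers (69 × 0.036 = 2.5) and none among active leavers gives 24 vs 11, p = 0.030. In this scenario the handling of leavers decides which side of 0.05 the result falls.

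**The case against.** Several replies have force.

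- **No text says every leaver is scored event-free.** A reader might infer that blanket rule from the event definition. It is only what 5.7.1 implies, and Appendix 10.1 contradicts it for symptomatic subjects with a missed swab. The supportable charge is an unstated and conflicting rule.
- **The result is robust at the design rates.** This stands. Twelve of 69 is 17%, over three times the assumed active rate, with no placebo leaver having an event. The 1980 is also a minimum. SAP 2.1 expects about 2459 subjects in the first-step analysis. With the SAP's 90% in Cohort A and 70% seronegative, 2459 × 0.9 × 0.7 = 1549, about 774 per arm with 77 leavers, and by the same method the tipping point is 15 of 77 (70 vs 50 events, p = 0.058).
- **Low-rate fragility depends on the active count.** A reader might infer that a handful of active-arm leavers would overturn the trial. The documents do not support that: the only low-rate data show no active events, and from 22 vs 0 it would take 11 of 69 active leavers to lose significance. Such readings also tend to assume no events among placebo leavers, which favours the tipping.
- **Losses may be limited and conservative.** Treatment is blinded, and subjects with confirmed infection stay under weekly testing and contact by flexible means. If infection drives departure, more placebo events would be lost, biasing towards no effect. This is plausible, but it is the kind of argument the promised analyses should test.
- **The endpoints are less inconsistent than they look.** For the weeks-based key secondaries, SAP 5.7.3 discounts a visit with missing RT-qPCR only when no broad-term symptom lies within 14 days. That agrees with Appendix 10.1. The disagreement is between 10.1 and 5.7.1.

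None of this supplies the missing analyses or reconciles the three SAP statements.

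**Conclusion.** The concern holds in this form. The missing-data sensitivity analyses that the synopsis announces appear in neither document; nothing planned tests how withdrawal affects either primary result; and SAP 5.7.1, Appendix 10.1 and Appendix 10.4 do not agree on missing primary-endpoint data. These conclusions rest on the text alone.

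The numerical consequence is modest under the design assumptions and uncertain outside them. At 10% vs 5% with 10% dropout in each arm, significance is lost only near 12 of 69 active-arm leavers against none on placebo. Margins shrink if the placebo rate is near 3.6% with a halved risk, or if dropout differs by arm. Those scenarios are illustrations: dropout by arm is not in the documents, household clustering is ignored, and no figures were worked for Cohort B. The plan should be changed before the first-step database lock, but nothing here shows the primary conclusion to be unsafe.

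**What to change.** 1. In SAP 5.7.1 and Protocol 11.4.3.1, state one rule for subjects with incomplete EAP follow-up and one for symptomatic subjects whose RT-qPCR is missing, covering both cohorts. Bring Appendices 10.1 and 10.4 into line. If the primary is not imputed, delete `by _imputation_` and the reference to 100 imputations from the primary code, and keep them for the any-infection key secondary.
2. In Protocol 11.4.3.1.1 and SAP 5.7.1.1, add a missing-data sensitivity analysis for both primary endpoints: multiply impute the binary symptomatic outcome for subjects who leave the EAP without an event, and add a tipping-point table over the event rate among leavers in each arm. The synopsis sentence then becomes true.

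The cost is wording, one new imputation model and one table. The existing imputation code cannot be reused unchanged, because it imputes PCR status only. The model must also say how PCR history is used when subjects leave at different visits, and it needs an augmented or penalised likelihood in case active-arm events are sparse. The 100 imputations and Rubin combination can be kept. No new data are required.
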